The sponsor (or designee) will review with the investigator and relevant site personnel the procedures for documenting receipt of IP, as well as the procedures for counting, reconciling IP, and documenting this process. Used (and/or empty) syringes of enoxaparin will be destroyed locally. Unused syringes will be destroyed locally after sponsor's approval for destruction. Documentation of all used and unused drug disposal must be maintained on site for review during monitoring visits.

Contraindications

Enoxaparin is contraindicated in patients with active major bleeding, in patients with thrombocytopenia associated with a positive in vitro test for anti-platelet antibody in the

presence of enoxaparin sodium, or in patients with hypersensitivity to enoxaparin sodium. Patients with known hypersensitivity to heparin or pork products should not be treated with enoxaparin or any of its constituents.

Warnings and Precautions

Enoxaparin is not intended for intramuscular administration. Enoxaparin cannot be used interchangeably (unit for unit) with UFH or other LMWH as they differ in manufacturing process, molecular weight distribution, anti-Xa and anti-IIa activities, units, and dosage. Each of these medicines has its own instructions for use. Enoxaparin should be used with extreme caution in patients with a history of HIT. Please refer to package insert for additional information.

Hemorrhage. Enoxaparin, like other anticoagulants, should be used with extreme caution in conditions with increased risk of hemorrhage. Cases of epidural or spinal hematomas have been reported with the associated use of enoxaparin and spinal/epidural anesthesia or spinal puncture resulting in long-term or permanent paralysis.

Major hemorrhages including retroperitoneal and intracranial bleeding have been reported. Some of these cases have been fatal. Bleeding can occur at any site during therapy with enoxaparin. An unexplained fall in hematocrit or blood pressure should lead to a search for a bleeding site.

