AEs can be 'Unexpected' or 'Expected'. Expected AEs include Bleeding development of HIT, pain from subcutaneous administration of the drug, and anemia from blood draws.

Unexpected AEs are those AEs occurring in one or more patients participating in the research protocol, the nature, severity, or frequency of which is not consistent with either:

- The known or foreseeable risk of AEs associated with the procedures involved in the research that are described in (a) the protocol-related document, such as the IRB-approved research protocol, any applicable investigator brochure, and the current IRB-approved informed consent document, and other relevant sources of information, such as product labeling and package inserts; or
- The expected natural progression of any underlying disease, disorder, or condition of the patient(s) experiencing the AE and the patient's predisposing risk factor profile for the AE.

AE Attribution

The participating site investigator must attempt to determine if an AE is in some way related to the use of the study drug and define an attribution category. This relationship should be described as follows:

- Definite – The AE *is clearly related* to the study treatment.

The event follows a reasonable temporal sequence from administration of the study drug, the event follows a known response pattern to the study drug and based on the known pharmacology of the study drug, the event is clearly related to the effect of the study drug. The AE improves upon discontinuation of the study drug and reappears upon repeat exposure.

- Probable – The AE *is likely related* to the study treatment.

The event follows a reasonable temporal sequence from administration of the study drug, the event follows a known response pattern to the study drug AND the event cannot have been reasonably explained by an intercurrent medical condition OR the event cannot be the effect of a concomitant medication.

- Possible – The AE *may be related* to the study treatment.

The event follows a reasonable temporal sequence from administration of the study drug and the event follows a known response pattern to the study drug BUT the event could have been produced by an intercurrent medical

condition which, based on the pathophysiology of the condition, and the pharmacology of the study drug, would be unlikely related to the use of the study drug OR the event could be the effect of a concomitant medication.

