site investigators within 15 calendar days.

A safety monitor is responsible for ongoing timely monitoring of reports of all SAEs submitted by site PIs, or other sources to ensure high-quality reporting, good clinical care and to quickly identify safety concerns. The identification of SAEs will begin when a member of the local research team reports an adverse event. The local research team will monitor each child daily for pre-defined adverse events, particularly clinically relevant bleeding. The research team will interview the clinical team and review the medical records daily for these events. The site PI or his/her designee will conduct prompt investigations of all reported adverse events, especially bleeding. All SAEs will be documented on a SAE form, entered in OnCore and communicated to the PM as soon as possible and <24 hours of the site PI knowing the event.

SAEs will be reported to the Yale Human Investigation Committee and the IRBs of the participating sites per policy.

Adverse Event Committee (AEC)

PI [name] will assemble an independent 3-member AEC composed of a pediatric hematologist (chair), a pediatric intensivist and a nurse. The responsibility of the AEC is to classify all AEs for publication and presentation purposes.

Minimizing Risks

To minimize the risk of bleeding, we will exclude children at high risk of bleeding. Enoxaparin will be held immediately and permanently after a clinically relevant bleeding event as defined by the International Society on Thrombosis and Hemostasis.⁵² Bleeding from enoxaparin can be reversed with protamine or administration of fresh frozen plasma. See section on Holding the Dose, which contains criteria for holding enoxaparin temporarily and when to restart the drug. Enoxaparin will not be replaced with another agent while the drug is on hold.

Platelet count will be monitored for the development of HIT. Enoxaparin and all heparin-related products will be held temporarily for unexplained decrease in platelet count.^{14, 53} Enoxaparin will not be restarted until the child tests negative for HIT.

Subcutaneous administration of enoxaparin may cause pain. As per local ICU practice, enoxaparin may be given through a subcutaneous catheter.

It is unlikely that the blood draws will result in anemia. Packed red blood cells can be transfused for anemia per the direction of the clinical team.

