The frequency of clinically relevant bleeding in critically ill children in the absence of anticoagulation is 0%-3% while that of children on prophylaxis with LMWH is 2.3%.^{43, 54-57} If ≥ 5 clinically relevant bleeding events (100 children \times 5.3% \approx 5 events) occur, the

safety monitor will notify the chair of the data DSMB. The DSMB chair may convene a meeting or teleconference of the DSMB to consider the concerns and plan appropriate action, including temporarily putting the trial on hold. Because of the difficulty in determining the relationship between bleeding events and enoxaparin in critically ill children, all bleeding events will be conservatively attributed to the drug unless the child has not received a dose for ≥ 30 hours, which corresponds to 5 half-lives of the drug.

CORRELATIVE SAMPLES

Blood

Blood for correlative studies will be drawn from the CVC into two 2.7 mL citrated tubes at the following four time points

1. Draw 1 (D1): <24 hours after insertion of CVC (and before enoxaparin is administered for subjects in the control arm)
2. Draw 2 (D2): 24±6 hours after D1 (or together with the blood draw for the anti-Xa activity for subjects in the treatment arm)
3. Draw 3 (D3): 4 days after insertion of CVC (if the child is still in the study at that time)
4. Draw 4 (D4): At the end of the study period

Blood will be processed locally using standard procedures for obtaining platelet-poor plasma. It will then be frozen at -70°C.⁵⁸ All specimens will be shipped to Yale for banking and will be analyzed every 6 months.

At any one of the time points specified above, additional blood will be drawn into one 0.5 mL EDTA tube for future genetic analysis. No processing is needed prior to freezing this sample.

Urine

At time points (D1-4) specified above for blood collection, 2-5 mL of urine will also be collected in urine collection tubes for correlative studies. No processing will be needed prior to freezing the urine locally at -70°C. Administration of enoxaparin should not be delayed if urine is not available before first dose of the drug is administered.

Please refer to laboratory manual for specific instructions on processing, storage and shipment of blood and urine samples to Central Laboratories for analyses and storage. Blinded personnel at each Central Laboratory will perform all assays in duplicate on platelet-poor plasma collected at all time points. Results will be averaged for analysis.

CORRELATIVE STUDIES

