Meeting format. The DSMB will meet as often as needed but the minimum will be at least once before the start of enrollment, after 10, 25 and 50 children have been enrolled, and after enrollment is completed (100 children enrolled). The DSMB will monitor the study according to guidelines specified in the research protocol and the operating procedures established at the initial meeting, unless the DSMB determines during the course of the study that modification of the guidelines is in the best interest of the study or the children in the study. The DSMB chair will set the meeting agenda. The DSMB members, the study statistician, project manager and the Sponsor PI will attend the session, at which time data concerning study conduct and aggregate safety data are discussed. Minutes of the meeting will be taken by staff of the DSMB.

Interim data summary reports. The study statistician will prepare data summary reports and send these directly to the DSMB members and the study team ≥ 7 days prior to the meeting. The report will focus on patient enrollment and demographics, data completeness, other study performance measures, and rates of serious adverse events. In addition to reports prepared by the statistician, PI [name] may prepare a report addressing concerns he anticipates the DSMB will have regarding the conduct of the study.

Communication of DSMB recommendations. At the conclusion of each DSMB meeting, the DSMB will provide a verbal report to PI [name] indicating areas of concern regarding performance and safety. Soon after the meeting, the chair will provide a written report to PI [name], including a summary of the DSMB's recommendations. In addition, the chair will provide a memorandum to PI [name] (including date of the meeting, a listing of data reviewed, recommendations, and date of

next review). PI [name] will forward this promptly to each participating site for submission to their IRBs, including the Yale Human Investigation Committee and the Project Management team.

The DSMB has the authority to recommend that the study protocol be terminated, temporarily suspended, or amended. This recommendation will be discussed with PI [name] before any action is taken. If the DSMB recommends a protocol amendment, the Yale Human Investigation Committee and site IRBs must approve the amendment before it is implemented.

Quality Management / Monitoring

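### The protocol requires no prompt notice to the DSMB of a single fatal or critical-organ bleed, a confirmed HIT case or a possibly drug-related death

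*Combined protocol and SAP*

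**What the plan says.** **The trigger.** Minimizing Risks sets the only written event-driven route to the board. "If ≥ 5 clinically relevant bleeding events" occur, the "safety monitor will notify the chair of the data DSMB. The DSMB chair may convene a meeting or teleconference of the DSMB". The count runs over all 100 children, both arms together.

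**Severity grades.** Appendix III already grades bleeds. Item 17 (major) includes fatal bleeds and bleeds in the abdomen or retroperitoneum, lung or CNS. Item 18 (clinically relevant non-major) covers bleeds needing blood products or an intervention outside the operating room. Item 19 is minor bleeding. The trigger does not use the split between items 17 and 18.

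**Safety outcomes.** Outcome Measures names three: clinically relevant bleeding, confirmed HIT and mortality.

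**SAE route.** Under AE Attribution and Procedure for Reporting Adverse Events, every SAE goes to the project manager within 24 hours and from there to the FDA. Further, "SAEs will be reported to the Yale Human Investigation Committee and the IRBs of the participating sites per policy". SAEs that are both unexpected and at least possibly related also go to the FDA within 15 days, the Yale committee within 5 days and site investigators within 15 days. A safety monitor follows SAE reports as they arrive. The DSMB is not named as a recipient.

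**Board review.** The Data safety and monitoring plan gives the DSMB sole authority for monitoring safety. It requires a review at least every six months, with SAEs in the board's report. Meeting format adds meetings before enrolment and "after 10, 25 and 50 children have been enrolled, and after enrollment is completed (100 children enrolled"), or more often if needed.

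**The concern.** The one body with authority over trial safety is not on the expedited route for the events most likely to need its judgement. If the text is followed exactly, a fatal or intracranial bleed on enoxaparin adds one to a count of five, and a confirmed HIT case or a possibly drug-related death adds nothing. Nobody is obliged to tell the board before its next scheduled review, and other children continue to be enrolled and dosed in the meantime. The Adverse Event Committee does not fill the gap, because its stated task is to classify events for publication and presentation.

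The protocol itself treats these events as possible. Its Warnings and Precautions state: "Major hemorrhages including retroperitoneal and intracranial bleeding have been reported. Some of these cases have been fatal".

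**Working it through.** **1. The plan's own figure.** 100 children × 5.3% = 5.3, rounded to 5. This reproduces. The protocol does not derive the 5.3%. It equals 3% + 2.3%, the upper untreated rate plus the LMWH rate given in the same paragraph. With 50 children per arm, those rates give 50 × 0.03 + 50 × 0.023 = 2.65 expected events, or 50 × 0 + 50 × 0.023 = 1.15 if the untreated rate is 0%. How the 5 was derived is a separate matter, and the point here does not rest on it.

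**2. How often the count is reached.** Assume at most one counted bleed per child and independent binomial counts in the two arms. P(total ≥ 5) is then:

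| Control rate | Enoxaparin rate | By child 50 | By child 100 |
|---|---|---|---|
| 0% | 2.3% | 0.02% | 0.6% |
| 3% | 2.3% | 1.0% | 12.7% |
| 0% | 10% (assumed) | 10% | 57% |
| 3% | 10% (assumed) | 22% | 79% |

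At the protocol's own rates, other bleeds are unlikely to bring a serious one to the board's notice by way of the count.

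**3. Fatal or critical-organ bleeds alone.** The documents give no rate, so these rates are assumptions. For 50 treated children, P(at least one) = 1 − (1 − p)^50, and P(at least five) is the binomial tail.

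| Assumed rate p | P(≥1 in 50) | P(≥5 in 50) |
|---|---|---|
| 0.5% | 22% | 0.0005% |
| 1% | 40% | 0.015% |
| 2% | 64% | 0.32% |

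One such event is plausible and five are not. A threshold of five therefore cannot act as a signal for them.

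**4. Wait for a scheduled review.** The Trial Summary gives 100 children in 21 months. Uniform accrual is an assumption: 100 / 21 = 4.76 children per month. Meetings after 10, 25, 50 and 100 children fall at 2.1, 5.25, 10.5 and 21 months, so the gaps are 2.1, 3.15, 5.25 and 10.5 months. The six-month minimum cuts the last gap to at most 6 months. In 6 months, 6 × 4.76 = 28.6 children are enrolled, and half of them, 14.3, receive enoxaparin.

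If enrolment takes 18 to 36 months (assumed range), the longest gap is still 6 months. The number enrolled in it runs from 6 × 100/18 = 33 down to 6 × 100/36 = 17, half of them on enoxaparin.

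**5. Routes side by side.**

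| Event | Required prompt notice outside the DSMB | Required prompt notice to the DSMB |
|---|---|---|
| Single fatal or critical-organ bleed | Yes, as an SAE | None until the count reaches five |
| Confirmed HIT | Yes, if it meets SAE criteria | None |
| Possibly drug-related death | Yes, as an SAE | None, except as one bleed in the count if it was a bleeding death |

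**The case against.** The case against is substantial, and much of it stands.

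- **The board is not kept in the dark.** Its periodic report includes SAEs and survival, and the statistician's interim reports cover SAE rates. A reader might infer that the DSMB never sees these events. The documents do not support that; only prompt notice is missing.
- **Fast review is possible.** The board may meet as often as needed and sets its operating procedures before enrolment, and the safety monitor is meant to spot concerns quickly. Those operating procedures are not in the documents and may contain a rule. This stands as a caveat. These provisions permit prompt review, but none requires anyone to tell the board about an event.
- **The count does have a severity floor.** Minor bleeds are excluded. It is only within clinically relevant bleeding that severity is ignored.
- **The affected child is protected.** Enoxaparin is stopped after a clinically relevant bleed or a HIT diagnosis. The gap concerns trial-level review only.
- **Expectedness does not cause the gap.** The AE Expectedness section says "Expected AEs include Bleeding development of HIT, pain from subcutaneous administration of the drug, and anemia from blood draws", and a reader might infer that serious bleeds are thereby removed from 24-hour reporting. They are not: all SAEs reach the project manager within 24 hours, expected or not. Expectedness governs only the 15-day FDA and investigator notices and the 5-day committee notice, and none of these is a route to the DSMB. The same section also counts severity when deciding what is unexpected.

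**Conclusion.** The point holds as a gap in required notification. Followed exactly, the written rule allows up to four fatal or critical-organ bleeds, and any number of confirmed HIT cases or possibly drug-related non-bleeding deaths, with no required prompt notice to the body that holds safety authority. Scheduled reviews would still show these events.

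The delay to a scheduled review is at most about 2.1, 3.15 and 5.25 months in the first three enrolment intervals, and about 6 months after child 50. The figure of about 29 more children, about 14 on enoxaparin, is a worst case. It needs an event just after a review, after child 50, with uniform accrual over 21 months. A reader looking only at the enrolment-based meetings might infer a wait of 10.5 months, but the six-month minimum review rules that out.

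The sponsor should make this change. It goes beyond missing detail, because the protocol writes a DSMB notification rule and that rule does not reach the gravest events.

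**What to change.** Add to Procedure for Reporting Adverse Events and Minimizing Risks that the safety monitor promptly (for example within 24 hours of receipt) forwards to the DSMB chair any report of:

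- a fatal or critical-organ bleed, using the protocol's own list of critical organs;
- confirmed HIT, as the protocol defines it;
- a death judged at least possibly related to study drug.

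The chair then records whether the board will convene. Keep the count of five alongside. This is a notification line only, and any decision on pausing or stopping stays with the DSMB. The definition of expected bleeding need not change. Because the safety monitor's stated task is to follow SAE reports, the text should also say how a confirmed HIT case not filed as an SAE reaches the monitor. If the DSMB's operating procedures already contain such a rule, citing it in the protocol would be enough.

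The cost is one paragraph in the protocol, mirrored in the operating procedures, using the existing safety monitor and board. The downside is an occasional extra teleconference for an event that proves unrelated to the drug.
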